## **Desing**

The study was designed and conducted as a two group quasi-experimental study. Intervention group (n=46) and control group (n=42) were administered the data collecting tools in the first assessment. After first assessment, the intervention group were included in the educational program. Data collecting tools were re-administered four weeks after to the intervention group only. Than data collecting tools were re-administered to the both groups in the postpartum 6th week.

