### **Data collection**

Data were collected by the first author (both control and intervention group). All data were collected with questionnaires conducted through face-to-face structured interviews with the data collector.

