#### *Secondary outcomes*

- Postpartum diabetes control of women with GDM was assessed through the postpartum 6th week information form that developed by the researchers on the basis of the literature.
- Postpartum characteristics of neonates were assessed through the neonate's information form that developed by the researchers on the basis of the literature.

The flowchart of this study is shown in Figure 1. The patients followed up in the perinatology clinic were assigned to groups through randomization (drawing lots by the clinic nurse). Data collector checked patients in the perinatology clinic daily. If there were more than one patient who met the inclusion criteria, it was determined which group to take with the lottery method. When there was only one woman with GDM in the clinic, it was determined which group to take with the lot but the next patient was taken directly to the opposite group. When two patients were in the same room, they were taken into the same group in order not to have any ethical problems. The women in the both group were administered the introductory information form, the HPLP-II, the CES-D and the SF-36 in the first assessment.

The education program and also usual care applied to the intervention group. The education program consisted of three 45-min sessions, which included a face-to-face lecture with the dissemination and presentation of written and visual materials. Also each participant in the intervention group was given the *Health-Promoting Lifestyle Booklet* and the *Diary of a Woman with GDM* card. The booklet features all of the health-promoting practices (self-monitoring of blood glucose, nutrition, physical activity, stress, sleeping, smoking, self-care and breastfeeding). The *Diary of a Woman with GDM* card features the daily program that women should follow (the hours for main meals and snacks, insulin hours, etc.). The education and counseling were maintained through follow-up via phone for intervention group.

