### **Data analysis**

The data were analysed using the SPSS 21 package. The introductory information derived from the introductory form administered to the participants in the intervention and the control group were analysed using descriptive statistical methods and compared using the Chi-square ( $\chi^2$ ) test and Mann-Whitney test. Pre-post test results of women in the intervention group were compared using the Wilcoxon Signed Rank Test. The first, second and third assessments of the intervention group were compared using the Wilcoxon Signed Rank Test, while the first and third (postpartum 6th month) assessments of the intervention and the control groups were compared using the Mann-Whitney test. Postpartum characteristics of the neonates were analysed using the Chi-square ( $\chi^2$ ) test and Mann-Whitney test. Lastly, the postpartum diabetes controls of the intervention and control groups were compared using Fisher's exact chi-square test.

[figure not shown]

Figure 1. Flowchart of this study

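### Women appear to be allocated before the first assessment, so the interviewer-administered baseline scores are potentially exposed to knowledge of the group

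*Combined protocol and SAP*

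**What the plan says.** The Secondary outcomes section of the combined protocol and SAP also holds the account of allocation and procedures. That account begins with allocation: "The patients followed up in the perinatology clinic were assigned to groups through randomization (drawing lots by the clinic nurse". It has the data collector looking for eligible women on the clinic every day and then gives three rules:

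- Where several eligible women are present, a lot decides.
- Where a woman is alone, a lot decides for her and the next woman goes to the other group.
- Women who share a room share a group.

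Only after these rules does the baseline appear: "The women in the both group were administered the introductory information form, the HPLP-II, the CES-D and the SF-36 in the first assessment".

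The Design section describes the baseline by group as well: "Intervention group (n=46) and control group (n=42) were administered the data collecting tools in the first assessment". It then says: "After first assessment, the intervention group were included in the educational program".

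On who collects the data, the Data collection section says "Data were collected by the first author (both control and intervention group" and "All data were collected with questionnaires conducted through face-to-face structured interviews with the data collector".

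In the Data analysis section, "The first, second and third assessments of the intervention group were compared using the Wilcoxon Signed Rank Test", and the two groups are compared by Mann-Whitney test at the first and third assessments.

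**The concern.** The HPLP-II, CES-D and SF-36 are subjective scales, and here they are completed in conversation with an interviewer. If the woman or the interviewer already knows the group, answers can shift before any education is given. Nothing in the plan requires that order, because the program starts only after the first assessment.

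The stake is the first assessment's role as a starting point. The second assessment, four weeks later, is described as the means of judging whether the program works, yet it is given to the intervention group only. On these scales the four-week evidence is therefore a within-group comparison with the first assessment, and no control group is measured at that time to reveal a distorted start. The comparison of first-assessment scores between groups is the plan's only check that the groups began alike on these scales, and it has the same exposure.

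**Working it through.** **1. Order.** Two places bear on it.

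| Section | What comes first | What follows |
|---|---|---|
| Secondary outcomes | Lottery, opposite-group rule, same-room rule | First assessment of women in both groups |
| Design | First assessment of groups already named (46 and 42) | Education of the intervention group |

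The first is the stronger evidence, because it is a step-by-step account. The second is compatible with it but does not settle timing. The Ethical considerations section places consent before inclusion without relating it to the lot. No section puts the baseline before the draw.

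**2. Knowledge of the group.** The nurse draws the lots, but the data collector screens the clinic and the first author interviews both groups. Under the opposite-group rule, the assignment after a lone patient is certain. Under the same-room rule, one woman's group fixes her roommate's. Many assignments could thus be known before the interview, and no section describes blinding or concealment.

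**3. Which analyses use the first assessment.**

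| Comparison in the Data analysis section | Uses first assessment? |
|---|---|
| Intervention group, first v second (Wilcoxon) | Yes |
| Intervention group, first v third (Wilcoxon) | Yes |
| Intervention group, second v third (Wilcoxon) | No |
| Between groups, first assessment (Mann-Whitney) | Yes |
| Between groups, third assessment (Mann-Whitney) | No |

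**4. Scale for the within-group tests.** The plan gives no figure on this point, so everything except the group sizes is assumed: no true effect, a baseline distortion of b SD in the intervention group that is absent later, equal SDs at both times, and pre-post correlation r. A normal approximation to a two-sided paired test at 0.05 stands in for the Wilcoxon test.

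- SD of the change = √(2(1 − r))
- k = b√46 / √(2(1 − r))
- P(significant) = Φ(k − 1.96) + Φ(−k − 1.96)

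Example, b = 0.2 and r = 0.5: SD of change = 1, k = 0.2 × 6.782 = 1.356, P = Φ(−0.604) + Φ(−3.316) = 0.274.

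| b (SD) | r = 0.3 | r = 0.5 | r = 0.7 |
|---|---|---|---|
| 0.1 | 0.088 | 0.104 | 0.141 |
| 0.2 | 0.209 | 0.274 | 0.417 |
| 0.3 | 0.405 | 0.530 | 0.748 |

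With no distortion each entry would be 0.05. A distortion that makes the baseline look worse produces apparent improvement. One in the other direction hides real improvement.

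**5. Would the baseline comparison reveal it?** For 46 v 42, SE = √(1/46 + 1/42) = 0.213 SD. Then P(significant) = Φ(b/SE − 1.96) + Φ(−b/SE − 1.96), which gives 0.076, 0.155 and 0.290 for b = 0.1, 0.2 and 0.3. A non-significant baseline test would give little reassurance.

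**The case against.** The strongest reply is that the order is read into the text. No sentence says the lot came before the first assessment, and Figure 1, which might show the sequence, is not available here. A report written in the past tense naturally labels women by the group they ended up in, and 46 and 42 may be final counts. All of this stands. It makes the point an inference, but one that follows the natural reading of the procedures and that no other section contradicts.

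A reader might also infer four stronger things that the documents do not support:

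- *That the interviewer is stated to have known the group.* The Data collection section says only that one person interviewed both groups. Knowledge is likely from the allocation rules, but it is not stated.
- *That all 88 women (46 + 42) were affected.* No section says when a woman learned her group, or that anyone withdrew on hearing it. At most, the women are potentially exposed.
- *That the between-group result at the third assessment is biased by this route.* That test does not use baseline scores. The same person collects that outcome too, but that is a separate matter.
- *That a false effect enters a change-score or baseline-adjusted comparison of the groups.* Neither analysis is in the Data analysis section.

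It can also be said that within-group changes without a control cannot establish efficacy whatever the baseline, and that predictable allocation is the deeper weakness. Both are fair. They limit what reordering achieves, but do not make a baseline taken after allocation harmless.

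**Conclusion.** The point holds as an inference about procedure: on the natural reading, the baseline follows allocation, and nothing described protects it from knowledge of the group. It should be corrected, but it is not a fatal flaw, and no actual distortion is shown.

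Its reach is limited to the three comparisons marked as using the first assessment. Its size cannot be known from the documents. On the assumptions stated in the working, even a 0.2 SD distortion would raise the false-positive rate of a within-group test from 5% to roughly 21-42%, while the baseline comparison would flag a shift of that size only about 16% of the time. Because the education came after the first assessment, the risk comes from knowing the allocation, not from exposure to the program.

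**What to change.** In the Design section and in the procedures text under Secondary outcomes, set the order as follows. For every eligible woman found that day, complete eligibility, consent, the introductory form and the first HPLP-II, CES-D and SF-36. Only then does the clinic nurse draw any lot, and only then is the group told.

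This needs the same forms, staff and visit, so the cost is the rewording. One limit remains: the opposite-group and same-room rules still let the collector, or a roommate, guess some assignments, so reordering reduces the exposure without removing it.

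The study is described as conducted in 2015. If the data are already collected, state the actual order and who knew the allocation at the first assessment. Unless the baseline did precede the draw, do not present first-assessment scores as a pre-allocation baseline. In either case, do not present the uncontrolled within-group changes as evidence of efficacy.

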- Women's level of knowledge about GDM was measured using pre-test and post-test question form. This form, developed by the researcher in accordance with the literature, includes questions about GDM and healthy lifestyle.

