The women in the control group which receiving only usual care were followed according to the institution's routine diabetes follow-up protocol (monitoring blood glucose levels as frequently as indicated by the doctor, and patients are referred to dietitian and to diabetes nurse). To assess the effectiveness of the educational program, the HPLP-II, CES-D and SF-36 were re-administered to the intervention group four weeks after the first assessment (second assessment). The HPLP-II, CES-D and SF-36 were re-administered to the both groups in the postpartum 6th week (third assessment).

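### The 4-week round meant to assess effectiveness has no control group, and the analysis section does not say that H1–H3 rest on the third-assessment group comparison

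*Combined protocol and SAP*

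**What the plan says.** The Design section (headed Desing) sets three assessments. At the first, "Intervention group (n=46) and control group (n=42) were administered the data collecting tools in the first assessment". At the second, "Data collecting tools were re-administered four weeks after to the intervention group only". At the third, HPLP-II, CES-D and SF-36 "were re-administered to the both groups in the postpartum 6th week (third assessment").

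The text under Secondary outcomes gives the second round its purpose: "To assess the effectiveness of the educational program, the HPLP-II, CES-D and SF-36 were re-administered to the intervention group four weeks after" the first assessment. It also says of the treatment: "The education program and also usual care applied to the intervention group".

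The Data analysis section compares the three assessments of the intervention group by Wilcoxon signed rank tests. It compares the two groups by Mann-Whitney test at the first and third assessments only, and there it places the third assessment at postpartum month 6 instead of week 6.

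Knowledge is listed under Primary outcomes: women's "level of knowledge about GDM was measured using pre-test and post-test question form". The Data analysis section plans a Wilcoxon test of pre-post results in the intervention group without naming the form. The list of first-assessment tools omits a knowledge form: "The women in the both group were administered the introductory information form, the HPLP-II, the CES-D and the SF-36".

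The Aim section states H1 (lifestyle), H2 (depressive symptoms) and H3 (quality of life) as claims that the program is effective. None of its four hypotheses concerns knowledge.

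**The concern.** The round expressly tied to effectiveness has no comparator. A change over four weeks in treated women alone contains whatever the program did, plus three things it did not do:

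- usual care, which the intervention group also received and which includes referral to a dietitian and a diabetes nurse;
- advancing pregnancy, since entry at 24–34 weeks puts the second round at about 28–38 weeks;
- answering the same questionnaires again.

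The intervention-only comparison of the first and third assessments has the same weakness, and it also spans delivery.

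The plan therefore holds uncontrolled and controlled tests of the same scales and does not say which set decides H1–H3. A report could support an effectiveness claim from the uncontrolled set alone.

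**Working it through.** **1. Who is measured, and how it is tested**

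| Outcome and time | Groups measured | Planned test |
|---|---|---|
| Three scales, first assessment | both | Mann-Whitney |
| Three scales, 4 weeks | intervention only | Wilcoxon, within group |
| Three scales, third assessment | both | Mann-Whitney; also Wilcoxon within the intervention group |
| Knowledge, pre and post | intervention; controls not stated | Wilcoxon within the intervention group, if this form is meant |

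**2. Number of tests.** Three assessments give 3 pairs. With one score per scale, 3 pairs × 3 scales = 9 possible uncontrolled tests, plus 1 for knowledge if that form is meant, against 3 controlled comparisons at the third assessment. One score per scale is an assumption: Primary outcomes gives total-score ranges for HPLP-II and CES-D, but for SF-36 it lists eight subscales and no total. Counting those eight gives 1 + 1 + 8 = 10 scores, hence 30 uncontrolled tests against 10 controlled. The ratio stays 3 to 1.

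**3. What drift does when the program has no effect.** The group sizes, 46 and 42, come from the Design section. The drift s and the correlation r between assessments are assumed, because the documents give neither. Scores have SD 1 and tests are two-sided at 0.05.

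The paired difference has SD √(2(1−r)), so the Wilcoxon test rejects with probability of about Φ(√(3/π) · s√46 / √(2(1−r)) − 1.96).

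- s = 0.2, r = 0.5: 0.977 × 0.2 × 6.782 / 1 = 1.33, giving about 26%.
- s = 0.3, r = 0.7: 0.977 × 0.3 × 6.782 / 0.775 = 2.57, giving about 73%.

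Simulation with 20,000 trials per setting gives 25.7% and 71.3%. With s = 0 it gives 5%. The Mann-Whitney test on third-assessment scores stays at 4.8–5.1%, because drift common to both groups cancels. With 20% random loss (37 and 34 women) the ranges are 21–61% and about 5%.

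**4. If drift is not equal.** By the third assessment the intervention group had answered the scales at two earlier rounds and controls at one. Suppose, as an assumption, that the extra round alone shifts the intervention group by 0.1–0.2 SD, with no program effect. The standard error is √(1/46 + 1/42) = 0.2134.

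- Mann-Whitney: 0.977 × 0.1 / 0.2134 = 0.46 and 0.977 × 0.2 / 0.2134 = 0.92, giving 7% and 15%.
- Baseline-adjusted: 0.1 / (0.2134 × √(1−0.5²)) = 0.54 and 0.2 / (0.2134 × √(1−0.7²)) = 1.31, giving 8% and 26%.

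**5. Room sharing.** The plan says: "When two patients were in the same room, they were taken into the same group". If every woman were paired in this way, the simulated Mann-Whitney error rate is 5–6% for an assumed intraclass correlation of 0.05–0.10, and about 7% at 0.20.

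**6. The plan's own figure.** The minimum of 30 per group at 80% power comes without an effect size, SD, outcome or sidedness, so it cannot be reproduced. Nothing above depends on it.

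**The case against.** The strongest reply is that H1–H3 already have a controlled comparison. The purpose clause is one sentence, followed at once by the assessment of both groups. The Aim section sets no 4-week hypothesis, and the Data analysis section contains no rule that turns a within-group change into a program effect. This stands. A reader might infer that the plan attributes the 4-week change to the program, or that H1–H3 have no controlled test. The documents support neither. What remains is that effectiveness is tied to the uncontrolled round and the controlled test is nowhere made decisive.

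A second reply is that the third-assessment comparison has weaknesses of its own. This also stands. The intervention group had the extra testing round. Part of the allocation was predictable, because after a lone patient was allocated by lot the next went to the opposite group. Same-room women were kept together. The first author interviewed both groups face to face. The error rate of about 5% assumes equal drift and does not cover predictable allocation or interviewer influence. The comparison is the better evidence because it is the only planned one on these scales with a control group, not because it is free of bias.

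A third reply is that baseline adjustment is a separate matter, and that replacing a planned test after data collection invites selective analysis. The fix respects this.

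On knowledge, a reader might infer that controls never received the form. The documents do not settle it: the Design section says both groups received the data collecting tools, the later list leaves the form out, and Figure 1 is not available here.

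**Conclusion.** The point holds in limited form and should be fixed. For the three scales, confidence is high: the second round is intervention-only, its tests are within-group, and no test is named as deciding H1–H3. A 4-week effect of the program cannot be claimed from the planned tests. For knowledge, confidence is moderate: on the natural reading no program effect can be claimed, but this rests on matching an unnamed pre-post test to the knowledge form.

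The defect follows from the design and needs no simulation. The simulated rates show only how far the two kinds of test can part under assumed drift and correlation. A significant Wilcoxon result in that setting is a correct detection of change over time; it misleads only when read as effectiveness.

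**What to change.** 1. State in the Data analysis section that H1–H3 are judged on the between-group comparison at the third assessment, and reconcile week 6 with month 6. Report the comparison adjusted for the first-assessment score (linear or rank-based analysis of covariance) together with the planned Mann-Whitney test. If data are already collected, as the past tense and the study's own Cronbach's alpha values suggest, declare the adjusted analysis post hoc and keep the Mann-Whitney test as the deciding one.
2. Label all intervention-only Wilcoxon tests (4-week, first-to-third, and knowledge if uncontrolled) as descriptive and not evidence of effectiveness. Compare knowledge between groups only if control data exist.
3. Name the SF-36 score or subscales that decide H3.
4. State the limits of the third-assessment comparison: the extra testing round in the intervention group, the partly predictable allocation, same-room placement, and interviews of both groups by the first author.

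The cost is text and one additional analysis of scores already held for both groups; no new data are needed. The price is that no 4-week effect, and probably no knowledge effect, of the program can be claimed. As an illustration of what adjustment adds, with an assumed benefit of 0.5 SD, r = 0.5–0.7 and 46 and 42 women, simulated power is 76–90% adjusted against 62% for Mann-Whitney; with 20% loss it is 66–82% against 52–53%. That gain is not a reason to change the deciding test after the data are in.

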## **Aim**

The aim of the study was to examine the effects of the **HPLEP** on maternal and neonatal health.

Hypotheses of this study;

H1: The **HPLEP** is effective for women with GDM in their adoption of a healthy lifestyle.

H2: The **HPLEP** is effective in reducing the symptoms of depression in women with GDM.

H3: The **HPLEP** is effective in improving the quality of life of women with GDM.

H4: The **HPLEP** is effective in reducing postpartum neonatal complications.

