## **Sample**

This study was conducted in the perinatology clinic of the Istanbul Zeynep Kamil Hospital, Turkey in 2015. The records show that 350 women with GDM were referred to the perinatology clinic in that period. The sample size was calculated using Power and Sample Size Program, with 80% power and a 0.05 margin of error, and it was

determined that both the intervention and the control group should include at least 30 women with GDM. It was considered appropriate that 50 women with GDM be included in each group.

The inclusion criteria for participation in the study included a gestational period of 24 to 34 weeks, a diagnosis of GDM, an age of 18 years or older, and voluntary consent to participate in the study, while the exclusion criteria included the presence of a psychiatric disease, multiple pregnancy, the risk of preterm labor, placenta previa or premature rupture of the membranes, and failure to obtain voluntary consent to participate in the study.

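### After baseline, the groups are compared on HPLP-II, CES-D and SF-36 only postpartum; the four-week assessment in pregnancy has no control data, so no change during pregnancy can be attributed to the program

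*Combined protocol and SAP*

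**What the plan says.** The Aim section states H1 to H3 as effects in women with GDM on lifestyle, depressive symptoms and quality of life. H3, for example, claims that the program "is effective in improving the quality of life of women with GDM". None of the three names a time point.

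The three scales are given as follows.

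- **First assessment.** Both groups, before the program: "Intervention group (n=46) and control group (n=42) were administered the data collecting tools in the first assessment" (Desing section; the Secondary outcomes section agrees).
- **Second assessment.** "Data collecting tools were re-administered four weeks after to the intervention group only" (Desing section). The Secondary outcomes section repeats this and introduces the visit as the means of judging whether the program works.
- **Third assessment.** "The HPLP-II, CES-D and SF-36 were re-administered to the both groups in the postpartum 6th week (third assessment" (Secondary outcomes section). The Desing section gives the same time.

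The Data analysis section plans Mann-Whitney tests between the groups at the first and third assessments only. The second assessment enters only a Wilcoxon signed rank comparison within the intervention group. The same section places the third assessment in the sixth month after birth, not the sixth week.

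**The concern.** Much of the program is about managing GDM day to day while pregnant. It covers self-management of blood glucose, and its diary "card features the daily program that women should follow (the hours for main meals and snacks, insulin hours, etc". The plan also schedules an effectiveness reading during pregnancy, at the one visit where the control group is not measured.

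Two things are at stake. A benefit that is present in pregnancy and fades after birth would not appear in any controlled comparison. And an improvement in the intervention group at four weeks could be reported as a program effect when it may reflect advancing gestation, usual care or filling in the same questionnaires again. This affects three of the four hypotheses and the scales listed as primary outcomes. H4, on neonatal complications, is not affected.

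**Working it through.** **Who is measured when**

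| Assessment | Intervention | Control | Between-group test planned |
|---|---|---|---|
| First (baseline) | yes | yes | yes, but before the program |
| Second (four weeks) | yes | no | no |
| Third (postpartum) | yes | yes | yes |

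The only controlled follow-up is the third assessment.

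**Timing.** Inputs: entry at 24 to 34 weeks of gestation (Sample section); second assessment four weeks after the first (Secondary outcomes section); birth at 40 weeks (assumption).

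- Second assessment: 24 + 4 = 28 weeks to 34 + 4 = 38 weeks of gestation.
- Pregnancy remaining after entry: 40 − 34 = 6 weeks to 40 − 24 = 16 weeks.
- Third assessment at postpartum week 6: 6 + 6 = 12 to 16 + 6 = 22 weeks after baseline.
- Third assessment at postpartum month 6 (about 26 weeks): 6 + 26 = 32 to 16 + 26 = 42 weeks after baseline.

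Under either date, the controlled follow-up comes after birth.

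**Can the one-group visit stand in for a controlled one?** A simulation set the program effect to zero and let scores drift between the first and second assessments. It used normal scores and 3000 runs per setting, with group sizes of 46 and 42 from the Desing section. The drift and the within-woman correlation are assumptions; the documents give neither. At correlation 0.5 the proportion of trials rejecting at 0.05 was:

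| Drift (SD) | Wilcoxon, intervention group only | Mann-Whitney, 46 vs 42, same visit |
|---|---|---|
| 0 | 5% | 5% |
| 0.1 | 11% | 5% |
| 0.2 | 25% | 5% |
| 0.3 | 50% | 5% |
| 0.5 | 90% | 5% |

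For a drift of 0.2 SD, the Wilcoxon rate ran from 19% (correlation 0.3) to 37% (correlation 0.7). The Mann-Whitney rate stayed at about 4 to 5% in every setting.

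**Would a controlled four-week comparison be large enough to be useful?** The plan's own figure comes first. The Sample section sets the calculation "with 80% power and a 0.05 margin of error" and "determined that both the intervention and the control group should include at least 30 women with GDM". No effect size, SD, outcome, time point or sidedness is given, so the 30 cannot be reproduced. It can only be solved backwards (two-sided 0.05, normal approximation):

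- d = √(2/30) × (1.960 + 0.842) = 0.258 × 2.802 = 0.72 SD. With one-sided testing the implied value is about 0.64 to 0.66 SD.
- With 46 vs 42 and no attrition, the difference detectable at 80% power is √(1/46 + 1/42) × 2.802 = 0.213 × 2.802 = 0.60 SD.
- Power with 46 vs 42 is 92% for 0.72 SD, 65% for 0.5 SD and 29% for 0.3 SD.

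A four-week comparison would therefore have more than the planned power for the difference implied by the plan's minimum of 30, though little for small differences. The design point itself does not depend on these figures.

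**The case against.** A reader might infer more: that because GDM belongs to the pregnancy, a postpartum assessment cannot test H1 to H3 at all. The documents do not support that. The hypotheses name no period. The Secondary outcomes section itself applies the label of women with GDM to an outcome taken at postpartum week 6, so it can be read as naming a population. Several program topics, such as breastfeeding, self-care, sleep and smoking, extend past birth, and HPLP-II covers general lifestyle domains. The postpartum comparison is thus a legitimate controlled test of lasting effect. Nor would it be right to call it the only controlled measurement, since the first assessment also covers both groups; it is the only controlled follow-up.

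Three practical objections also have force. The document is written in the past tense about a study run in 2015, so four-week control data may no longer be obtainable. A woman who enters at 34 weeks and delivers before 38 weeks would have the four-week visit after birth. And the plan does not say when the three sessions or the telephone follow-up end, so a four-week visit may come before the program is complete.

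The gap in pregnancy remains. The plan introduces the four-week visit as a test of effectiveness, and without control data it cannot be one.

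**Conclusion.** The concern holds as a limit on what can be claimed. The trial can compare the groups on a lasting postpartum effect in women who had GDM. It can describe before-after change in the intervention group at about 28 to 38 weeks of gestation, but it cannot attribute that change to the program, because 0 of 42 control women are measured then.

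The conclusion rests on the assessment schedule and the planned tests, on which the Desing, Secondary outcomes and Data analysis sections agree. The 12 to 22 week interval to the controlled follow-up (32 to 42 if month 6 is meant) assumes birth at 40 weeks. The rejection rates under drift are illustrations that depend on assumed values. The documents contain no results or conclusion, so nothing here says that a pregnancy effect has in fact been claimed.

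**What to change.** 1. In the Desing and Secondary outcomes sections, give HPLP-II, CES-D and SF-36 to both groups four weeks after the first assessment.
2. In the Data analysis section, add the between-group comparison at that visit as the test of effect during pregnancy, and keep the postpartum comparison as the test of lasting effect. Attach a time point to each of H1, H2 and H3. State how women who deliver before the visit are handled.
3. Reconcile the sixth week with the sixth month for the third assessment.

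The cost is one more questionnaire session per control woman: 42 on the numbers at first assessment, up to 50 on the planned size ("It was considered appropriate that 50 women with GDM be included in each group"). The Data collection section has one person interviewing both groups. The plan does not say whether that person could absorb the extra sessions. Both groups would then complete the scales the same number of times; at present it is three against two. Some late entrants may deliver before the visit.

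If four-week control data cannot be obtained, report the second assessment as descriptive only and limit the H1 to H3 conclusions to the postpartum time point, with no claim of effect during pregnancy. This needs no new data, but it narrows the claim.
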